## **MRI PROCESSING GUIDELINES**

**Overview:** All MRI studies will be blindly evaluated by at least two experienced neuroradiologists (Drs. [name] and [name]). If there is an urgent or emergent finding obtained by the research MRI study, this will be communicated by one of the neuroradiologists directly to the ENT physician for follow up who is caring for the patient, as per normal departmental protocol. In the case of this study, incidental findings are defined as anything not already noted in the medical record.

**Methodology of MRI Evaluation:** The research MRI study of the head and neck will be performed on a Siemens 3T MRI Scanner system located in the Center for Clinical Imaging Research (CCIR). Multiplanar / multisequence MRI data including the optimized research DWI sequence will be acquired. MRI subjects must complete an MRI screening evaluation form before entering MRI zone 3 or the scanning room. Images will be anonymized and sent to CNDA for archiving after diagnostic reports are complete. All anonymized MRI studies will then be blindly evaluated by at least two experienced neuroradiologists (Drs. [name] and [name]). MUSE image processing will be applied post-acquisition.

**Methodology of ADC Evaluation:** The primary tumor, suspicious lesion, and/or area of post-treatment change will be first identified in the anatomical images and then outlined in the ADC sequence by experienced neuroradiologists (Drs. [name] and [name]), excluding areas of cystic change and necrosis. If there are multiple lesions, only the dominant lesion with the lowest ADC will be utilized for analysis, akin to RECIST criteria. If there is geometric distortion, a region of interest will be placed in the undistorted region only. A histogram analysis method will be used to examine the distribution of ADC values within each region of interest (ROI). Only measurable disease defined as a primary tumor, a suspicious lesion, and/or an area of post-treatment change measuring at least 0.5 cm in two perpendicular dimensions will be used. Technically poor or non-diagnostic MR images will be excluded. ADCmean/min will be computed.

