## 7.0 STATISTICAL CONSIDERATION

### STATISTICAL ANALYSIS

Study Design and Endpoints: This is a pilot study designed as a paired, prospective, single-blinded study in which we compare the sensitivity and specificity of the optimized DWI sequence ADCmean/min versus FDG PET/CT SUVmax for the evaluation of recurrent SCC in post-treatment patients. The primary endpoints of sensitivity and specificity will evaluate the diagnostic accuracy of the optimized DWI sequence ADCmean/min versus the standard-of-care FDG PET/CT SUVmax. The secondary endpoint will evaluate if the enhanced DWI sequence can more expediently assess non-responders to treatment as compared to FDG PET/CT.

Aim 1: The 60 subject sample size for this pilot study was chosen for feasibility of recruitment based on the approximately 650 PET/CT exams performed for head and neck tumor in 2018. ROI will be used for statistical assessments of ADC measurements (see methodology of ADC measurement, above). FDG-PET SUVmax results will be used as the reference standard for tumor or non-tumor tissue. ADCmean, ADCmin and standard deviation will be used to describe distribution of ADC measurements (AADC) in tumor and non-tumor tissues and independent sample t-test will be used to compare ADC measurements between the two groups. Mean difference and 95% confidence interval around that will be used to interpret our results. For ROC analysis, the area under the curve (AUC) will be calculated and the Youden's J index will be used to identify the value of the predictor variable that optimized sensitivity and specificity. Youden's J index varies from 0-1. The threshold value that provides the value of the J index closer to 1 is the value with the best performance and discriminative power. PPV and NPV will also be evaluated. The logistic regression model allows for evaluating this impact after controlling for potential confounders. We will explore the linearity assumption of relationship of delta ADC with logit of outcome (response to treatment) and if the assumption is violated,

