polynomial effects will be explored, and data transformation will be employed as needed. All statistical analysis will be carried out by [name], a biostatistician in the ENT Department with extensive experience in head and neck cancer research. A 90% confidence interval will be calculated for the differences in sensitivity and specificity of the enhanced DWI sequence ADCmean/min as compared with the standard-of-care FDG PET/CT SUVmax. The positive and negative predictive values will also be evaluated. Since this is a pilot study, no existing data can be utilized to calculate a power analysis.

A binary logistic regression model will be utilized to evaluate the impact of the change in ADC in predicting early non-responders to treatment. A p-value will be calculated to evaluate if the enhanced DWI sequence can more expediently identify non-responders to treatment as compared to FDG PET/CT.

(\*\*Note: Patients who do not undergo SOC PET/CT at the 3-6 month time point will be considered inevaluable and will be replaced.)

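### The only rule for calling ADC positive is a Youden cut-off chosen and scored in the same patients, with no validation planned, so the primary DWI sensitivity and specificity would be too high on average.

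*Combined protocol and SAP*

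**What the plan says.** All references are to the combined protocol and SAP.

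- **Primary endpoints** (section 7.0, Study Design and Endpoints): "The primary endpoints of sensitivity and specificity will evaluate the diagnostic accuracy of the optimized DWI sequence ADCmean/min", set against PET/CT SUVmax.
- **Cut-off** (section 7.0, Aim 1): after an ROC analysis, "the Youden's J index will be used to identify the value of the predictor variable that optimized sensitivity and specificity". The section adds: "The threshold value that provides the value of the J index closer to 1 is the value with the best performance and discriminative power".
- **ADC measurement** (MRI Processing Guidelines, Methodology of ADC Evaluation): rules for the region of interest, the choice of lesion and minimum size, then "ADCmean/min will be computed". It gives no ADC threshold and no visual positive/negative reading rule.
- **PET** (PET/CT Imaging Processing Guidelines): literature SUVmax values are given, above 9.0 for a primary mass and above 4.5 for nodal tumor. There is no counterpart for ADC.
- **Intervals** (section 7.0): "A 90% confidence interval will be calculated for the differences in sensitivity and specificity of the enhanced DWI sequence ADCmean/min" relative to PET. The interval method is not named.
- **Reference standard**: section 7.0 says "FDG-PET SUVmax results will be used as the reference standard for tumor or non-tumor tissue". Section 2.0 names histology and/or one-year outcome instead.
- **Sample size**: 60, chosen for feasibility, with no power calculation.

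**The concern.** ADC is continuous, so sensitivity and specificity do not exist until a cut-off is set. If the cut-off is the one that looks best in these patients, and accuracy is then counted in the same patients, the estimate benefits from chance features of this sample that will not recur. Nothing in the plan corrects for this or warns the reader.

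The study is a pilot with no success criterion, so no formal decision goes wrong. What is at stake is interpretation and later planning. Section 2.0 says that a good result could change imaging follow-up. A later study built on these figures would start from accuracy that the same cut-off should not be expected to reach in new patients.

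**Working it through.** **There is no plan figure to reproduce.** The 60 patients come from feasibility, and the documents give no expected AUC or tumor prevalence. Both are assumed below.

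**Direction.** Let Ĵ(c) be observed sensitivity + specificity - 1 at cut-off c, J(c) its true value, and ĉ the chosen cut-off. With an empirical search the reported value is the maximum of Ĵ(c) over c. Then E[max Ĵ(c)] ≥ max J(c) ≥ E[J(ĉ)]. The first step holds because a mean of maxima is at least the maximum of the means. The second holds because no chosen cut-off can beat the best one. Apparent J is therefore too high on average.

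**Size, empirical search.** Monte Carlo with 5000 replicates, n=60, one metric, binormal ADC with equal variances and mean shift √2·z(AUC). The Youden cut-off is placed midway between observations. Truth is the accuracy of that same cut-off in new patients. Entries are mean apparent minus true: J; sensitivity points; specificity points.

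| AUC | 20% tumor | 30% tumor | 40% tumor |
|---|---|---|---|
| 0.70 | 0.158; 12.6; 3.2 | 0.134; 9.4; 4.1 | 0.128; 7.6; 5.3 |
| 0.80 | 0.140; 11.3; 2.7 | 0.119; 8.4; 3.6 | 0.109; 6.6; 4.3 |
| 0.90 | 0.120; 9.6; 2.3 | 0.100; 6.9; 3.0 | 0.092; 5.5; 3.7 |

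Worked case, AUC 0.80 and 30% tumor:
- Shift = √2 × 0.842 = 1.190.
- Best achievable J = 2Φ(0.595) - 1 = 0.448.
- The data-chosen cut-off achieves 0.420 on average in new patients.
- The study would report about 0.420 + 0.119 = 0.54.

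Over the nine settings PPV is inflated by about 5 to 8 points and NPV by 3 to 6. J is overstated in 86-92% of simulated trials, so the bias is an average and not a certainty in any one trial. With an uninformative marker (AUC 0.50, 9 to 30 of 60 with tumor), apparent J still averages about 0.15 to 0.20.

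**Size, other estimator.** If the cut-off comes from a fitted binormal ROC with unequal variances (4000 runs, AUC 0.70-0.90, 12 to 24 of 60 with tumor), J optimism is only about 0.01 to 0.03. The fitted model matches the simulated data here, so this is a favourable case. Section 7.0 does not say which estimator it will use.

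**What could enlarge it.**
- Fewer analysed patients. "Technically poor or non-diagnostic MR images will be excluded", as are lesions under 0.5 cm, whereas the replacement rule covers only missing PET: "Patients who do not undergo SOC PET/CT at the 3-6 month time point will be considered inevaluable and will be replaced". At AUC 0.80 and 30% tumor, empirical J optimism is 0.13 at n=50 and 0.15 at n=40 (both n assumed).
- Keeping the better of ADCmean and ADCmin (correlation 0.7 assumed; AUC 0.70-0.90, 9 to 30 with tumor). Inflation is then 6.0 to 19.0 points for sensitivity and 2.6 to 7.8 for specificity.

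**Intervals for DWI's own accuracy.** These 90% intervals, on apparent counts with an empirical cut-off, are centred too high. The lower limit should lie above the truth in 5% of trials.

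| Method | Sensitivity: lower limit above truth | Specificity: lower limit above truth | Sensitivity coverage |
|---|---|---|---|
| Wilson | 12-20% | 9-15% | 80-88% |
| Exact | 6-13% | 6-11% | 87-94% |

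**Does correction work?**
- Ten-fold cross-validation, with the cut-off re-chosen in each fold, leaves a mean bias of -0.7 to +0.5 points in sensitivity and within 0.3 points in specificity. A preset cut-off is within 0.4 points, which is simulation noise.
- Leave-one-out leaves -0.012 to +0.005 in J.
- Root mean squared error of J, leave-one-out against apparent, at AUC 0.80: 0.176 v 0.180 at 20% tumor, 0.162 v 0.157 at 30%, 0.159 v 0.148 at 40%.
- A bootstrap repeating leave-one-out in each resample covers sensitivity in only 77-92% of trials (60 resamples per trial, so a rough figure).

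**The case against.** **The plan never says that the primary estimates use the Youden value.** This is true, and a reader should not infer that it does say so. But ADC needs some cut-off and the documents contain no other. If a different rule was meant, then the scoring rule for the primary endpoints is missing, and the first step of the fix is still needed.

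**It is a pilot, and finding a candidate cut-off is a normal pilot aim.** This also stands, and it limits the harm. The plan already includes the AUC and the mean ADC difference with a 95% interval. The cut-off choice distorts neither, provided the AUC is for one metric named in advance. Pilot status excuses the missing power calculation; it does not remove bias from endpoints called primary.

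**The size is uncertain.** This stands in full. AUC, prevalence and the ROC estimator are all open, and a well-fitting smooth ROC makes the bias small.

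**PET is the reference, so DWI gains nothing over PET.** A reader might infer that a fitted ADC cut-off tilts the comparison towards DWI. Under section 7.0's reference it cannot. PET judged against itself scores 100%, so DWI minus PET cannot exceed zero; the inflation is in DWI's agreement with PET, and the difference merely lies too close to zero. A tilt towards DWI arises only with the section 2.0 reference and PET read at fixed values such as those in the PET/CT guidelines. Its size should not be quoted, because it depends on where those values fall. At PET AUC 0.80, moving the PET cut-off 0.5 SD stricter than its optimum changes PET sensitivity/specificity from 72.4%/72.4% to 53.8%/86.3%.

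**Conclusion.** The concern holds for DWI's own accuracy figures. Followed as written, and with the Youden value used because no other rule exists, the plan gives sensitivity, specificity, J, PPV and NPV that are too high on average. The upward direction appeared in every setting tried. Under the stated assumptions (n=60, one metric, AUC 0.70-0.90, 20-40% tumor, binormal ADC) the inflation with an empirical search is about 0.09 to 0.16 in J, 5 to 13 points in sensitivity and 2 to 5 in specificity. With a correctly specified fitted binormal ROC it is about 0.01 to 0.03 in J.

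The documents do not support three stronger readings: that the DWI-versus-PET comparison is biased in DWI's favour under section 7.0, that the AUC of a pre-named metric or the mean difference is inflated, or that the larger range applies whatever the ROC method. The sponsor should correct this before analysis. It does not call the conduct of the study into question.

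**What to change.** In section 7.0, state how ADC is called positive for the primary endpoints and name the ROC estimator. Then choose one option.

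- **(A) Preset.** Fix one ADC metric and one cut-off before the reference results are seen. The documents contain no such value, so one must be justified from elsewhere. A moderate miss costs little: at AUC 0.80, J in new patients is 0.436 if the preset value is 0.25 SD off its optimum and 0.401 if 0.5 SD off, against 0.420 on average for the data-chosen cut-off.
- **(B) Cross-validate.** Keep the Youden cut-off. For each ADC metric, report cross-validated sensitivity, specificity, PPV and NPV beside the apparent values, redoing the cut-off (and any choice between metrics) in every fold. Label the cut-off and its accuracy exploratory until tested in new patients. State that the 90% intervals are approximate and that intervals on apparent counts are centred too high. Do not present a bootstrap with repeated leave-one-out as restoring 90% coverage.

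The conflict over the reference standard between sections 2.0 and 7.0 is a separate matter and should be reconciled first, since it decides what the accuracy figures mean.

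Cost: a SAP paragraph and a little code, with no extra patients or scans. Under (B) the reported DWI accuracy will be lower. The gain is less bias, not more precision: the estimates are somewhat more variable, and root mean squared error of J is slightly higher at 30-40% tumor.

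### The non-responder model is ordinary logistic regression on few events, with no limit on covariates and a data-chosen ADC form; this overstates the ADC effect, and a Firth-penalised fit would largely correct it

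*Combined protocol and SAP*

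**What the plan says.** Section 7.0, Statistical Analysis, sets the sample on practical grounds: "The 60 subject sample size for this pilot study was chosen for feasibility of recruitment". On power it says: "Since this is a pilot study, no existing data can be utilized to calculate a power analysis".

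The model serves the secondary endpoint. The plan states: "A binary logistic regression model will be utilized to evaluate the impact of the change in ADC in predicting early non-responders to treatment". On adjustment: "The logistic regression model allows for evaluating this impact after controlling for potential confounders". On the shape of the ADC effect: "We will explore the linearity assumption of relationship of delta ADC with logit of outcome (response to treatment) and if the assumption is violated", then "polynomial effects will be explored, and data transformation will be employed as needed". The output is a test: "A p-value will be calculated to evaluate if the enhanced DWI sequence can more expediently identify non-responders to treatment as compared to FDG PET/CT".

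The plan does not give an expected number of non-responders, a list or maximum number of covariates, a test or threshold for the linearity check, a penalised or exact fitting method, any internal validation, or a significance level. Section 4.0, Clinical Data to be Collected, lists fields that could serve as covariates (age, sex, stage, location, HPV status, smoking, treatment types) but does not link them to the model. Section 4.0, MRI Processing Guidelines, excludes technically poor images and lesions below a minimum size without stating replacement, so fewer than 60 patients may be modelled.

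**The concern.** Maximum-likelihood logistic regression is biased away from zero when events are few relative to model terms, and the bias grows with each added term. Here the events are a fraction of at most 60 patients and the number of terms is open. Naming the covariates would not remove the bias. It depends on the count of terms and on the estimator, and it arises whichever ADC measure is the predictor.

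Choosing the form of the ADC term from the same data and then testing it gives ADC a second chance to reach significance, so the reported p-value no longer has its nominal meaning.

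At stake are the ADC odds ratio and its p-value. Because the plan has no prior data for a power calculation, these estimates are natural inputs for the next study, and an inflated odds ratio would make that study too small.

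**Working it through.** **No figure to reproduce.** The only stated number is 60, set by feasibility. What follows rests on labelled assumptions.

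**Events.** Events = 60 × non-response rate. At 20%, 30% and 40% this is 12, 18 and 24. At 10% it would be 6. The rates are assumptions.

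**Events per term**, for one linear ADC term plus k covariates = events / (1 + k):

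| Covariates k | 12 events | 24 events |
|---|---|---|
| 0 | 12 | 24 |
| 2 | 4.0 | 8.0 |
| 4 | 2.4 | 4.8 |
| 7 | 1.5 | 3.0 |

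**Bias of the ADC coefficient.** Simulated trials of 60 patients, 12-24 expected events, true odds ratio 2.5 per SD of ADC (log odds ratio ln 2.5 = 0.916), linear ADC term only. The last column is exp(0.916 × (1 + overstatement)).

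| Covariates k | Overstatement of log odds ratio, maximum likelihood | Odds ratio that this implies |
|---|---|---|
| 0 | 8-10% | 2.7 |
| 2 | 14-15% | 2.8-2.9 |
| 4 | 20-23% | 3.0-3.1 |
| 7 | 26-42% | 3.2-3.7 |

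A Firth-penalised fit of the same model, at each size, is within about 4% of the truth (odds ratio about 2.4-2.6) and has lower root mean squared error. With two covariates and 12 events, for example, it falls from 0.55 to 0.43.

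A separate simulation used a true log odds ratio of 0.80 and 2, 4 or 6 covariates that do affect the outcome (log odds ratio 0.3 each). Maximum likelihood overstated the linear ADC term by 22%, 31% and 43% at 12 events and by 13%, 23% and 27% at 24. Firth gave a mean of 0.78-0.82.

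**False positives when ADC has no effect.** The conditional rule was simulated as the text reads: add a quadratic only if its likelihood-ratio test gives p < 0.05, then test ADC at 5% two-sided (the plan states no level). There were 800 trials per case.

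| Covariates k | 12 events | 24 events |
|---|---|---|
| 0 | 10.2% | 7.8% |
| 2 | 9.5% | 6.9% |
| 4 | 13.6% | 10.2% |
| 6 | 13.9% | 11.2% |

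Not all of this excess comes from choosing the form. With six covariates and 24 events, a fixed linear term already rejects in 7.6% of trials. The coefficient itself averages close to zero when there is no effect, so the harm in that case is to the p-value.

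**Discrimination, if reported.** With a true log odds ratio of 0.80 and the conditional rule, the adjusted model's AUC in its own data against new patients is 0.77 against 0.69 (two covariates, 12 events) and 0.82 against 0.70 (six covariates, 24 events). With ADC alone the gap is about 0.01. Firth does not close it: with ADC and two covariates at 12 events, the figures are 0.77 against 0.68 with either estimator.

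**The case against.** The strongest reply is that the plan states no model size. A careful analyst might adjust for two covariates, at 4 to 8 events per term, where the bias is 14-15%. Most of the gain in precision would then come from keeping the model small. In a run of 1,000 trials at 12 events, root mean squared error was 1.02 with seven covariates under maximum likelihood, 0.58 with two, and 0.44 with two under Firth. This stands. Model size is the larger lever, but the estimator still matters at a fixed size.

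A reader might go further and infer that the plan's model would give an odds ratio of 3.2-3.6 and an apparent AUC of 0.81-0.84 against 0.64-0.65 in new patients. The documents do not support that. Those figures come from a nine-term model with seven covariates and a squared ADC term forced into every fit. No covariate count is stated, and the list of collected data is not a model specification. The squared term enters only if linearity is judged violated, which in the conditional simulation happened in about 5-11% of trials with a linear truth. The nine-term result is an upper-end scenario.

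A reader might also take the planned AUC to be that of the adjusted model. Section 7.0 describes ROC analysis and Youden's index for the predictor variable, before it turns to logistic regression. No AUC of the adjusted model is promised.

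Checking linearity is sound practice. The objection is only to letting the check decide which result is reported.

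**Conclusion.** The point holds. With 12-24 events, the stated method overstates the ADC log odds ratio by about 8-10% with no covariates and by up to 26-42% with seven, and nothing in the plan keeps it at the lower end. A Firth fit of the same model is within about 4%. Under no ADC effect, the data-chosen form contributes to a false-positive rate of about 7-14% against a nominal 5%.

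These sizes rest on assumptions that the documents do not supply: a non-response rate of 20-40%, a true odds ratio of 2.5 per SD (2.2, that is exp(0.80), in the separate simulation), the covariate counts, and a 5% two-sided level. The direction does not depend on them, except that the coefficient is not biased when the true effect is zero.

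The consequence is limited. This is a secondary endpoint of a pilot that makes no power claim, and the primary sensitivity and specificity are unaffected. Separately, the model is written for change in ADC, while the section 4.0 calendar schedules a single DWI MRI. Those passages must be reconciled, but the point applies to whichever ADC measure is used.

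**What to change.** In section 7.0:

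- Fit the non-responder model by Firth-penalised likelihood, with profile-likelihood confidence intervals.
- Make a single linear ADC term, per SD, the reported model.
- Add a small number of covariates, chosen by the investigators in advance and in line with the expected number of non-responders. The documents do not single out which these should be.
- Keep the linearity check, and report any polynomial or transformed form as a labelled sensitivity analysis.
- If discrimination of the adjusted model is reported, give a bootstrap optimism-corrected AUC, because Firth does not remove that optimism.

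The cost is plan wording and standard software, with no new data. The downside is that some recorded confounders stay unadjusted, and a truly curved ADC effect would appear only in the sensitivity analysis.

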## 2.0 OBJECTIVES

The Specific Aim of this application is as follows: To compare SUVmax and ADCmean/min values to assess the capability of the new DWI pulse sequence to differentiate post-treatment change from residual or early recurrent tumor.

Hypothesis: The optimized research DWI pulse sequence obtained up to 3 weeks post treatment will accurately identify residual/recurrent tumor, as confirmed by the clinical FDG PET/CT obtained at 3-6 months. This would potentially result in a modification of imaging follow-up algorithms, increased cost-savings and eliminate radiation exposure to patients inherent in PET/CT. This would also result in earlier changes to treatment regimens and stratify patients into more or less aggressive tumor response to treatment. The gold-standard will be histological tissue where available and/or 1-year clinical and imaging outcomes, including imaging outcome measurements such as RECIST 1.1 [De Bree, 2017], PERCIST [Joo Hyun, 2016] and iRECIST [Persigehl, 2020].

**Figure 1:** DWI data obtained from a healthy volunteer with a GE 3 Tesla system and eight-channel neurovascular array coil. Single-shot EPI-based DWI was obtained: matrix size = 128  $\times$  128; parallel imaging acceleration factor = 2; field of view = 24 cm  $\times$  24 cm; b-value = 1000 s/mm^2. B, High-resolution DWI data obtained with four-shot interleaved EPI pulse sequence (matrix size = 256  $\times$  256; field of view = 24 cm  $\times$  24 cm; b-value = 1000 s/mm^2) and reconstructed with our developed MUSE algorithm.

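### DWI and PET are compared only on sensitivity and specificity, with no common operating point and no paired AUC difference, so a difference may reflect where each marker was cut

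*Combined protocol and SAP*

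**What the plan says.** Section 2.0 sets the aim: "To compare SUVmax and ADCmean/min values to assess the capability of the new DWI pulse sequence" to tell post-treatment change from residual or early recurrent tumor. Section 7.0 describes the design: "This is a pilot study designed as a paired, prospective, single-blinded study". It then names the endpoints: "The primary endpoints of sensitivity and specificity will evaluate the diagnostic accuracy of the optimized DWI sequence ADCmean/min versus the standard-of-care FDG PET/CT SUVmax". The comparison itself is one sentence: "A 90% confidence interval will be calculated for the differences in sensitivity and specificity of the enhanced DWI sequence ADCmean/min", with PET SUVmax as comparator.

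Both markers are continuous, so each must be cut before it has a sensitivity or a specificity. The documents give two pieces of information on cut-offs:

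- Section 7.0, Aim 1: "Youden's J index will be used to identify the value of the predictor variable that optimized sensitivity and specificity". The sentence names no marker. ADC is the evident predictor, because the same paragraph makes SUVmax the reference.
- Section 4.0, Methodology of SUV Evaluation: literature SUVmax values, above 9.0 for a primary mass (interquartile range 7.4–13.9) and above 4.5 for nodal tumor. Nothing says that these define a positive PET in the Section 7.0 comparison.

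One AUC is planned, with no marker named. No difference in AUC between the markers is planned.

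**The concern.** Sensitivity and specificity depend on the marker and also on where it is cut. Two markers with identical ROC curves, cut at different points, have different sensitivities and specificities, usually with opposite signs: one gains sensitivity and gives up specificity. If the plan does not put the two markers at comparable points, and has no comparison free of the cut-off, the two planned differences cannot be separated into accuracy and threshold placement.

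Section 2.0 foresees changed imaging follow-up algorithms and less PET/CT radiation if DWI performs well. A result in which DWI is ahead on one measure and behind on the other, from cut-offs chosen by different rules, would neither support nor refute that.

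This is separate from the optimism of choosing a cut-off on the study data. It arises even with both cut-offs fixed beforehand.

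**Working it through.** There is no planned power or effect size to reproduce. The plan says "The 60 subject sample size for this pilot study was chosen for feasibility of recruitment" and that "no existing data can be utilized to calculate a power analysis".

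**Inputs from the documents.** n = 60, paired; two 90% intervals (z = 1.645), one for sensitivity and one for specificity.

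**Assumptions, not in the documents.** Both tests have the same true AUC of 0.80, are equal-variance binormal, and have within-patient correlation 0.3. There are 12 to 18 tumors among the 60, scored against an independent reference. Both cut-offs are fixed, so no optimism enters.

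**Step 1, the common ROC curve.** Separation d = √2 × Φ⁻¹(0.80) = 1.414 × 0.842 = 1.19. The Youden point is at d/2 = 0.595, where sensitivity = specificity = Φ(0.595) = 0.72. DWI is placed there.

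**Step 2, PET elsewhere on the same curve.** For PET specificity s, the cut-off is c = Φ⁻¹(s) and sensitivity is Φ(d − c). Example, s = 0.85: c = 1.036 and sensitivity = Φ(0.154) = 0.56. DWI minus PET is 0.724 − 0.561 = +0.16 in sensitivity and 0.724 − 0.85 = −0.13 in specificity.

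**Step 3, how often an interval excludes zero.** Simulated trials, with paired Wald intervals and 0.5 added to the discordant counts:

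| PET specificity | Sensitivity difference (points) | Specificity difference (points) | At least one 90% interval excludes 0 |
|---|---|---|---|
| 0.60 | −10 | +12 | about 47% |
| 0.72 (same point as DWI) | 0 | 0 | 16–17% |
| 0.80 | +9 | −8 | 33% |
| 0.82 | +12 | −10 | 42–43% |
| 0.85 | +16 | −13 | 57–60% |
| 0.90 | +26 | −18 | about 86% |
| 0.95 | +40 | −23 | 99% |

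The fair baseline is 16–17%, because two 90% intervals are examined. Anything above it comes from cut-off placement alone.

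**Step 4, a comparison without cut-offs.** Under the same assumptions a paired DeLong 90% interval for the AUC difference excludes zero in about 10–11% of trials, close to its nominal 10%. Its mean half-width is about 0.12–0.14.

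**Step 5, does Youden for both tests solve it?** No. Over AUC 0.80 and 0.90, correlation 0.3 and 0.5, and 20–40% tumors, reading both tests at cut-offs chosen on the study data gives mean differences near zero. Even so, 34–51% of trials have at least one uncorrected interval that excludes zero, because the intervals ignore the choice of cut-off.

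**Step 6, the reference standard.** Section 7.0, Aim 1 makes SUVmax the reference for tumor; Section 2.0 names histology and/or 1-year outcome. Under Aim 1, PET has sensitivity, specificity and AUC of 1 by construction. A DWI sensitivity of 0.80 then gives 0.80 − 1 = −0.20 whatever PET's real accuracy, and steps 1 to 5 do not apply.

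**The case against.** The strongest reply is that sensitivity and specificity are the declared primary endpoints. With cut-offs fixed beforehand, the differences are true differences at those cut-offs, and a trade-off is a legitimate finding. The plan attaches no hypothesis test, superiority claim or decision rule to the intervals, and this is a 60-patient feasibility pilot. That stands. It is why the AUC difference should support the primary endpoints and not replace them. It does not remove the need to state the cut-offs, or to have one analysis that separates accuracy from threshold placement.

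Three stronger readings are tempting, and the documents do not support them:

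- A reader might infer that the 90% intervals use a Youden cut-off for ADC and the cited SUV values for PET. Section 7.0 never links the Youden rule to the intervals, and Section 4.0 cites the SUV values only as literature.
- A reader might infer that AUC is planned for ADC alone. That is likely, but the sentence names no marker.
- A reader might infer that equally accurate tests will usually look different. In the table this passes one half on the high-specificity side only between 0.82 and 0.85, and no document figure fixes where PET will sit. Nor is a clear split, with both intervals excluding zero in opposite directions, the typical result: it occurs in 10–12% of trials at specificity 0.85, 32–38% at 0.90 and 69–79% at 0.95.

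**Conclusion.** The concern holds as a gap in the plan. The only accuracy comparison of DWI with PET rests on two cut-offs that are not fixed at a common operating point, and no paired AUC comparison is planned. The differences may therefore reflect cut-off placement. The size depends on an SUV rule that the documents do not state: from the 16–17% baseline when the tests are cut at the same point to 99% when PET is cut at specificity 0.95, against about 10–11% for a paired AUC difference. These figures rest on the assumed AUC, correlation, tumor count and fixed cut-offs, and on both tests being scored against an independent reference. That last condition is not met while Section 7.0 uses SUVmax as the reference, so the conflict with Section 2.0 comes first.

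**What to change.** 1. Reconcile Section 7.0, Aim 1 with Section 2.0 so that both markers are scored against the Section 2.0 gold standard. Without this, neither the planned comparison nor an AUC comparison is meaningful.
2. State in Section 7.0, before the data are seen, the cut-off or cut-off rule for each marker in the sensitivity and specificity comparison. If a rule is applied to the study data, the interval should allow for that, for example by a bootstrap that re-selects the cut-off.
3. Add to Section 7.0: *ADC and SUVmax, both kept continuous, will also be compared by the paired difference in AUC (DeLong method) with a 90% confidence interval, and by sensitivity at matched specificity. A difference in sensitivity or specificity will be interpreted as a difference in accuracy only alongside this AUC difference.*

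Sensitivity and specificity remain the primary endpoints. The cost is some wording and a supportive analysis on data already collected; no patients or procedures are added. The downside is that AUC is less directly clinical and, with a half-width of about 0.12–0.14 under these assumptions, imprecise at n = 60.
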